## 7.0 OVERVIEW OF STUDY PROCEDURE AND SCHEDULE:

Procedures	Visit 1	Visit 2	Visit 3	Visit 4	Visit 5
Explain the study, answer questions and consent	x				
Medical history questionnaire (form will be updated at Visits 2-5)	x	x	x	x	x
Anthropometric measurements (height and weight)	x	x	x	x	x
FIT Core (bone & muscle imaging, physical function testing, and questionnaires)	x				
Assigned to Group and provided instructions.		x		x	
Complete 3-day Food Record prior to visit		x	x	x	x
Return Stool Sample		x	x	x	x
Physical Activity Questionnaire		x	x	x	x
Sun Exposure Questionnaire		x	x	x	x
Bowel function and gastrointestinal tolerance questionnaires collected			x		x
Fasting Blood Collection		x	x	x	x
Compliance calendar collected			x		x
Honorarium (\$50 gift card after each visit is completed)	x	x	x	x	x

## 8.0 STUDY PROCEDURES:

**Health and Medical History.** Relevant medical history will be obtained at Visit 1 by the Study Coordinator. The information collected will include a brief medical history, questions related to health behaviors, reproductive history, bone health history (i.e., incidence of previous fractures), prior oral contraceptive and hormone replacement use, as well as the use of other medications and supplements (*See Medical History Form*). The health and medical history will be updated at each subsequent visit to account for any changes occurring over the course of the study. Any concerns raised will be brought to the attention of the CRC staff physician for recommendations.

**FIT Core.** At Visit 1, participants will complete assessments at the FIT Core (IRB study #1707550885). This will include but is not limited to providing additional information related to their medical history, medications, and body composition (height, weight). They will be asked to answer questionnaires regarding their physical function and physical activity and will undergo a DEXA or bone density test. Participants will also be asked to complete a battery of tests related to their physical capacity, including hand grip strength, repeated chair stands, gait speed, timed up-and-go, a six-minute walk test, and a balance assessment.

**Blood Sample Collection.** Participants will provide fasting blood specimens, collected between 7:30-10:00 AM at baseline and final time points in each period (Visit 2-5). Whole blood (~21 mL) will be collected in CPT tubes (BD Biosciences) for FACS analyses and *ex vivo* experiments with PBMCs to characterize Th17 and Treg abundance and function. One additional tube (~5 mL) will be collected and processed for serum, and stored at -80°C for metabolomics, cytokines, 25(OH)D and bone biomarkers.

**Fecal Sample.** Participants will be asked to collect 2 stool samples prior to each visit (Visits 2-5) using a sample collection kit (DNA GeneTek). They will be also asked to rate their stool consistency using the Bristol Stool Scale, as well as ease of passage using a 5-point Likert scale (1 = very easy, 2 = easy, 3 = neither easy nor difficult, 4 = difficult, 5 = very difficult) as we have previously reported [49].

**Anthropometric Measurements.** Height and weight will be assessed at each visit and body mass index (BMI kg/m^2) calculated.

**Physical Activity Patterns.** Physical activity patterns will be assessed Visits 2-5 using the validated CHAMPS Physical Activity for Older Adults Questionnaire. This questionnaire is designed to elicit information on leisure, occupational, and home activities and classifies the activities based on duration. Participants will be asked to refrain from altering their physical activity from Visit 2 until the completion of the study at Visit 5. Physical activity data will be analyzed to determine usual activity level, consistency over time and deviations from baseline.

**Bowel Function and Gastrointestinal Tolerance.** At Visits 2 through 4, participants will be instructed to complete a validated questionnaire [50] about their bowel function and gastrointestinal tolerance each day throughout the treatment period. They will be asked to rate the severity of gastrointestinal symptoms—such as abdominal distention and nausea—on a 4-point scale (1 = absent, 2 = mild, 3 = moderate, 4 = severe). Participants will also record the date and time of each bowel movement. Stool consistency will be assessed using the Bristol Stool Scale, and ease of stool passage will be rated on a 5-point Likert scale (1 = very easy, 2 = easy, 3 = neither easy nor difficult, 4 = difficult, 5 = very difficult) [49].

**Dietary Assessment.** Prior to Visits 2-5, participants will enter their 3-day diet intake using ASA24 to include 2 weekdays and 1 weekend day. They will be instructed to measure (using standard measuring cups/utensils) and record all food, beverages and supplements consumed. At least two of the three days

should include the days immediately prior to their visit to coincide with fecal collections. [name], who is an RD, will assist with developing these instructions. Participants will be asked to refrain from making changes to their routine diet or supplement intake throughout the study. They will also be instructed to try to consume the same foods in the days preceding their final visit of each study period as they reported at baseline to minimize the influence of dietary factors on outcomes. The 3-day record will be analyzed by study personnel using the ASA24 tool. Dietary assessment will be performed to assess dietary pattern, energy intake, and macronutrient and select micronutrient composition.

**Consumption of Dried Plums and Compliance.** The test product will be provided by the CA Dried Plum/Prune Board in commercially prepared snack bags. During the 1-week run-in to the dried plum intervention period, participants will be instructed to gradually increase their consumption of dried plum over 1 week following a schedule of 2 dried plums/d for 2 days (1 after breakfast and 1 after dinner), 4 dried plums/d for 3 days (1 after breakfast, 1 after lunch and 2 after dinner), followed by 6 dried plums/day (2 each after breakfast, lunch and dinner). Participants will be instructed to try to continue to spread the consumption of 50 g of dried plum throughout the day during the 4-wk intervention period and to consume their final dried plums at ~9:00 PM prior to their study visit. Suggestions will be provided with the assistance of [name] about ways to incorporate dried plums into the diet, without cooking. To assess compliance with the dried plum, each participant will be given a calendar to record the date and time that the fruit was consumed. The Study Coordinator will contact participants weekly by text or email to encourage compliance and note any adverse events. At the final visit, participants will return their calendar and any unused dried plum as indicators of compliance.

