#### *Exclusion Criteria.*

- women who have been on medications known to alter bone or calcium metabolism (e.g., oral bisphosphonates, raloxifene, denosumab, intermittent parathyroid hormone, growth hormone) within 12 months of starting the study. Prior use of intravenous bisphosphonates at any time.
- women who have been on hormone replacement therapy, steroids (i.e., glucocorticoids), biologics, or chronic NSAID within 3 months of starting the study.
- women with a previous diagnosis of osteoporosis (i.e., BMD T-score or history of vertebral fracture or fragility fractures of hip, wrist, humerus after the age of 50 yr) or other metabolic bone disease (e.g., osteomalacia or osteogenesis imperfect), renal disease, stroke, heart attack, type 2 diabetes, liver disease or autoimmune diseases (e.g., rheumatoid arthritis, systemic Lupus erythematosus, type 1 diabetes mellitus, IBD) that could affect bone metabolism or T cell biology will be excluded.
- women who have undergone treatment for cancer within 12 months of starting the study
- women who have been taking prebiotic or probiotic supplements or natural products that have estrogen-like effects in the past 3 months
- women who smoke, have a BMI  $>40$  kg/m $^2$  or  $<18.5$  kg/m $^2$ , or consume  $\geq 2$  alcoholic drinks per day
- women who regularly consume dried plums or prune juice ( $>1$  serving weekly).

[figure not shown]

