The primary study (Visits 2-5) is divided into three phases, with each lasting about 4 weeks (**Figure 1**). Prior to returning for Visit 2, participants will record their 24-hr dietary intake over three days using the Automated Self-administered 24-hour (ASA24) dietary assessment tool. At Visit 2, participants will return their stool sample, and baseline data collection will be performed that includes anthropometrics, questionnaires, any updates to the medical history questionnaire and a blood draw. Participants will then be randomly assigned to the AB or BA intervention sequence using a computer-generated list of random numbers. Instructions will be provided on the run-in protocol and incorporating dried plum into the diet (50 g/day or 5-6 dried plums per day) or not based on their sequence. Study personnel will provide the dried plums in snack packs at no cost. Note the snack packs will be provided by the California Prune Board. At Visit 3, participants will complete the data and sample collection as described for Visit 2 and then begin the washout period. Visit 4 will be scheduled following the washout period and the same procedures described in Visit 3 will be repeated with crossover to the second intervention. At Visit 5 (final visit), participants will complete the data and sample collection. At Visits 3 or 5, any remaining dried plums will be returned. All procedures will strictly adhere to the guidelines set forth by the Indiana University School of Medicine Institutional Review Board. The study will be registered with ClinicalTrials.gov.

**Figure 1. Overview of Experimental Design.** Postmenopausal women ( $n >= 30$ ) will be randomized to one of two treatment sequences (AB or BA) and complete 5 study visits (*details below*). Each treatment period (Phase 1 & 3) will consist of an approximately 1-wk run-in followed by 4 wks of treatment with a 3-4 wk washout in between.

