## **11.0 STATISTICAL CONSIDERATION:**

**Power Calculation.** Although we anticipate a low attrition rate due to the utilization of an effective run-in period as previously described [35], we conservatively incorporated a 10% attrition rate in our power calculation. Our sample size has 80% power to detect an effect size of 0.8 standardized mean difference in the immune response between the treatment with dried plum and control (i.e., no dried plum). Based on a previous study of the anti-inflammatory effect of dried plum in a similar population of postmenopausal women consuming 50 g/d [51], an effect size of approximately 1.5 SD was observed for serum IL-6 when comparing the dried plum group to the control group. Thus, our study sample size (n=30) provides adequate power to detect expected treatment effects. Power estimation was conducted our by biostatistician and co-PD, *[name]*, using PASS v19.

**Statistical Analyses.** De-identified data will be analyzed using PC SAS version 9.4 and SAS PROC MIXED, GLIMMIX, and GLM. Descriptive statistics will be calculated for all variables and will include means, SD, medians, and minima/maxima. Distributions of outcome variables will be examined graphically using histograms and box plots for symmetry and for outliers. Logarithmic transformation will be applied to non-normally distributed data. For our primary outcomes, we will use linear mixed effects models to determine if the level of serum IL-6 and T cells (i.e., Th17) at the end of each period is significantly different for dried plum compared to the control. Baseline measures, treatment and period indicators,

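### Women who eat up to one serving of dried plums or prune juice a week may enter and are told to keep their usual diet, so the control period, the washout and the reference samples can contain the test food; the effect is modest.

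*Protocol*

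**What the plan says.** Four places in the Protocol bear on this.

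- **Eligibility (Section 4.0, Exclusion Criteria).** The criterion covers "women who regularly consume dried plums or prune juice", with regular use defined as more than one serving weekly. A woman at one serving a week, or less, is eligible.
- **Background diet (Section 8.0, Dietary Assessment).** "Participants will be asked to refrain from making changes to their routine diet or supplement intake throughout the study". Women are also asked to "try to consume the same foods in the days preceding their final visit of each study period as they reported at baseline". Neither instruction exempts dried plums or prune juice.
- **Assignment (Section 6.0).** Instructions are given on "incorporating dried plum into the diet (50 g/day or 5-6 dried plums per day) or not based on their sequence". The washout is described only by its length: "1-wk run-in followed by 4 wks of treatment with a 3-4 wk washout in between".
- **Control (Section 11.0, Power Calculation).** The comparison is "between the treatment with dried plum and control (i.e., no dried plum".

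**The concern.** The trial compares plum with no plum within each woman, and the exclusion criterion shows that the sponsor regards habitual intake as a threat to that comparison. The criterion nevertheless leaves a permitted remainder, and the diet instruction asks women to maintain it. The repeat-foods request sharpens this: a woman who recorded prunes before the baseline visit of her control period is asked to try to eat them again just before the samples that close that period.

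At stake is whether the control period, the washout and the reference samples are free of the test food, as Section 11.0 describes for control. This matters most for Objective 2, which looks at stool taxa and at fecal and serum metabolites. A recent serving could show up in those measures even when the weekly average is small.

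**Working it through.** **1. The instructions side by side, for a woman who eats one serving a week**

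| Stage | Instruction that applies | Non-study plums if followed exactly |
|---|---|---|
| Before Visit 2 | Section 4.0 admits her; nothing asks her to stop | Can be present |
| Control period | Section 6.0 says not to incorporate dried plum; Section 8.0 says keep the routine diet | Two instructions pull apart; own product and juice not mentioned |
| Washout | Section 8.0 only | Can be present |
| Dried plum period | Section 8.0, plus the study plums | Can be present on top of the study dose |
| Days before a period's final visit | Section 8.0 repeat-foods request | Requested again if reported at that baseline |

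**2. Size relative to the test dose**

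- Test dose: 50 g a day (Sections 6.0 and 8.0), so 7 × 50 = 350 g a week.
- Serving size: not in the documents. Assume 40-50 g of dried fruit. No equivalent for juice can be derived from the documents.
- Largest permitted share: 40/350 = 11.4% to 50/350 = 14.3%.

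**3. Effect on the contrast**

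Let x be her own weekly intake, and assume that response is proportional to dose.

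- She keeps x in both periods, as Section 8.0 asks: (350 + x) − x = 350 g a week. The contrast is unchanged.
- Study plums replace her own in the plum period: 350 − x = 310 g (x = 40) or 300 g (x = 50), that is 88.6% or 85.7% of the intended contrast.
- If the response saturates, the contrast can shrink even in the first case. The documents give no dose-response from which to size this.

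The loss is averaged over all women. If, for illustration, a quarter were at the limit and all replaced their own plums, the mean contrast would fall by 0.25 × 11.4% = 2.9% to 0.25 × 14.3% = 3.6%. The true share is not in the documents.

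**4. Chance that the diet records show it**

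There is a 3-day record before each of Visits 2-5. If the serving falls on a random day of the week, independently at each record, one record misses it with probability 4/7 = 57%, and all four miss it with probability (4/7)⁴ = 256/2401 = 11%. Most weekly consumers would thus be visible at least once. The records observe intake; they do not prevent it, and only the last few days of the washout are covered.

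**5. The plan's power figure**

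The stated 80% reproduces. With 30 women less 10% attrition = 27 completers, a difference of 0.8 SD, no within-woman correlation, 25 degrees of freedom and two-sided alpha 0.05, a crossover t-test has 80.6% power. Step 3 gives no reason to revise it, because the contrast is unchanged when the diet instruction is followed and the response is linear.

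**The case against.** The strongest reply is that Section 6.0 already tells women in the control period not to incorporate dried plum, and that Section 11.0 defines control accordingly. A specific rule may be read as qualifying a general one, and the sentence in Section 6.0 is not expressly limited to the supplied packs. Participant instructions are also still to be developed with a dietitian and are not at hand, so they may contain an avoidance rule. This stands as evidence of intent for the control period. It does not address self-bought product or prune juice, it does not cover the washout, and it leaves the keep-your-diet and repeat-foods instructions without an exception.

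The second reply is that a small, stable background intake under a constant diet is a defensible choice. This largely stands for the mean contrast, as step 3 shows. It is weaker for individual samples, where a weekly serving may fall before one visit and not another.

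Monitoring is also better than one record suggests. There are four records, at least two of the three days sit immediately before the visit, and a compliance calendar is collected at Visits 3 and 5. The Protocol gives the calendar's purpose as compliance with the study plums, does not say that it captures non-study intake, and schedules no calendar collection at Visit 4, the end of the washout.

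A reader might infer more: that the planned 0.8 effect drops to about 0.69-0.71, that power falls to about 68-71%, and that the bias always runs toward no effect. The documents do not support this. Those figures need every woman to be at the limit and every woman to drop her own serving during the plum period, which is the diet change that Section 8.0 asks her not to make. They also give no credit for within-woman correlation.

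**Conclusion.** The conflict in the text is real, and its consequence is modest. Followed exactly, the Protocol allows the test food into the control period, the washout and possibly the reference stool and serum samples of an eligible once-weekly consumer.

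The permitted amount is at most 11-14% of the weekly test dose, given the assumed serving of 40-50 g. Under a linear response and an unchanged diet the mean contrast is about intact. It is reduced only if study plums replace her own or the response saturates. A serving near a sampling day adds noise to stool and serum measures. The number of women affected is unknown. The case for a change rests on the inconsistency and on how cheaply it can be removed, not on lost power.

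**What to change.** Reconcile Sections 4.0, 6.0, 8.0 and 11.0. Add one exception to the diet instructions in Section 8.0, applying to both the keep-your-diet and the repeat-foods requests: dried plums and prune juice other than the study product are left out from before Visit 2 until Visit 5, and the rest of the diet stays as it was. This follows the Protocol's own plum-free definition of control and extends it to the washout.

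Add one item on non-study dried plum or prune juice intake to a form already in use, covering both periods and the washout. The medical history update is suitable, since it is completed at each of Visits 2-5 and so includes the end of the washout.

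The cost is one sentence, one form item and a trivial diet change for the few women concerned. No visits, samples or participants are added.

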## 9.0 POTENTIAL RISKS AND PROCEDURES FOR MINIMIZING RISK:

### Risk Associated with Blood Draws

The risks of drawing blood might be pain at the needle site, bruising, and feeling faint. Rarely is there a risk of infection. To reduce potential risks, blood will be drawn by experienced technicians using standard institutional practice and guidelines.

### Risk from Physical Ability Tests

Risks during or following the FIT Core physical ability testing (i.e., hand grip strength, chair stands, gait speed, walk test, isokinetic dynamometer, and balance assessment) include muscle soreness or cardiac ischemia due to physical activity. However, the protocol is not effort dependent, and participants are able to terminate the test at any time. In addition, the test is terminated if heart rate reaches 180 bpm in order to minimize the cardiac risk.

### Risk from DXA Scan

Exposure to a very small radiation dose occurs with DXA scanning. This amount of radiation is less than one tenth that of a chest x-ray and less than the natural radiation that one is exposed to during a normal day. Therefore, DXA scans are very unlikely to have a significant impact on health risks, but participants will be made aware.

### Risk of Gastrointestinal Issues/Distress

There is a chance that participants will experience changes in their bowel habits, the consistency of stools, and experience gas and bloating when consuming the dried plum. To minimize these effects, participants will be given details instructions about the run-in period for the dried plum arm of the study. This

approach has been shown in previous studies to almost eliminate the chance of these effects with the 50 g/d dose [35].

### **Risk of Developing an Allergy to Plums**

There is a remote possibility that a participant will develop an allergic reaction to consuming dried plums. Plums are related to cherries, peaches, nectarines, and apricots. The most common allergic reaction is itchy mouth and throat; however more severe reactions such as rash, difficulty breathing, nausea and vomiting, and anaphylactic shock can occur. If participants have known allergies to cherries, peaches, nectarines, or apricots, a small sample will be provided at the initial visit to monitor possibility for reaction.

### **Risk of Loss of Confidentiality**

There is a slight risk of loss of confidentiality of subject information. Every effort will be made to keep subject information confidential. Information collected will be maintained on secure, password protected electronic systems. Paper files that contain personal information will be kept in locked and secure locations only accessible to the study team. Samples that are collected will be identified by a participant study number assigned at the time of enrollment. Any material issued to researchers will be anonymized and only identified by a coded number.

## **10.0 STUDY WITHDRAWAL/DISCONTINUATION:**

Participants may elect to withdraw from the study at any time and for any reason by notifying the research personnel. Participants may also be withdrawn for incomplete data or failure to perform the visits as outlined within the specified protocol period.

## **11.0 STATISTICAL CONSIDERATION:**

**Power Calculation.** Although we anticipate a low attrition rate due to the utilization of an effective run-in period as previously described [35], we conservatively incorporated a 10% attrition rate in our power calculation. Our sample size has 80% power to detect an effect size of 0.8 standardized mean difference in the immune response between the treatment with dried plum and control (i.e., no dried plum). Based on a previous study of the anti-inflammatory effect of dried plum in a similar population of postmenopausal women consuming 50 g/d [51], an effect size of approximately 1.5 SD was observed for serum IL-6 when comparing the dried plum group to the control group. Thus, our study sample size (n=30) provides adequate power to detect expected treatment effects. Power estimation was conducted our by biostatistician and co-PD, *[name]*, using PASS v19.

**Statistical Analyses.** De-identified data will be analyzed using PC SAS version 9.4 and SAS PROC MIXED, GLIMMIX, and GLM. Descriptive statistics will be calculated for all variables and will include means, SD, medians, and minima/maxima. Distributions of outcome variables will be examined graphically using histograms and box plots for symmetry and for outliers. Logarithmic transformation will be applied to non-normally distributed data. For our primary outcomes, we will use linear mixed effects models to determine if the level of serum IL-6 and T cells (i.e., Th17) at the end of each period is significantly different for dried plum compared to the control. Baseline measures, treatment and period indicators,

vitamin D (i.e., serum 25-OH D), and important demographic characteristics (e.g., age, BMI, years post menopause) will be included as fixed effects. Random participant effects will be included to accommodate the correlations among repeated measures. We will test for a carry-over effects, but we assume there will be no effect after adjusting for baseline and period effects. We will perform a per protocol analysis on the primary outcomes, which includes only those who completed the intervention and who were compliant ( $\geq 85\%$ ) with the study protocol. Hypothesis tests for the treatment effect will be carried out following standard procedures for mixed-effects models [52]. Similarly, for secondary outcome measures (i.e., gut microbiota, metabolites, and bone resorption markers), we will use separate mixed effects models, adjusting for baseline, period, and demographic covariates. Categorical variables will be assessed using the generalized linear mixed-effects models. Importantly, to gain a better understanding of the gut-bone axis response, we will also integrate the immunologic outcomes (i.e., T cell), metabolomics, microbial taxa and bone biomarker data. These analyses will include regression analyses to correlate key outcomes. In addition, we will explore if dried plum consumption modulates the immune response via alterations in metabolite and microbiota profiles by conducting exploratory mediation analysis. For all statistical analyses, alpha will be set at 0.05.

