## 2.0 PROJECT GOALS AND OBJECTIVES:

The goal of this project is to understand how dietary supplementation with dried plums, a food with prebiotic activity, affects T effector cells (i.e., Th17 & Treg) and their function; and to explore whether vitamin D status of the host alters this response. The fundamental questions to be addressed are: 1) whether the findings of pre-clinical studies [26, 28, 47, 48] demonstrating the gut microbiota is a target to counter T cell changes associated with estrogen deficiency translate to postmenopausal women; and 2) whether the vitamin D status of the host influences the response to this prebiotic.

To accomplish this, we will recruit postmenopausal women, age 60-75 years, to participate in a randomized crossover control study with and without dried plum. Eligible volunteers who are willing to consume dried plum per day (5-6 dried plums/d), participate in an ~ 14-wk study, and meet all other inclusion/exclusion criteria, will be consented. We plan to enroll n>=30 women.

The *hypothesis* is that dried plum will have anti-inflammatory effects on the gut-bone axis of postmenopausal women, characterized by a decrease in the abundance of Th17 cells (i.e., increase in Treg/Th17 ratio) and their activation; and this response will be more pronounced in women with higher serum 25(OH) D. To date, there are no reports indicating how dried plum affects the abundance and function of Th17 cells, which accelerate bone resorption by osteoclasts that leads to postmenopausal bone loss and the influence of vitamin D on this response. To test our hypothesis, we will perform a randomized crossover control study designed to:

**Objective 1.** Determine how dried plum supplementation alters circulating T cells (e.g., Th17 & Treg cells), other immune cells that regulate T cell function (e.g., B regulatory cells), and the inflammatory response of postmenopausal women compared to a control period in a crossover design study. *Peripheral blood mononuclear cells (PBMC) will be isolated from whole blood collected pre- and post- treatment of each arm of the study and the change in T cell populations and their function as well as inflammatory mediators in response to dried plum will be assessed.*

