### **3.0 OUTCOME MEASURES AND ENDPOINTS:**

The **primary outcomes** of this study will be change in circulating Th17 cells and their function in *ex vivo* experiments, and inflammatory cytokines (e.g., IL-6 & IL-17).

**Secondary outcomes** will include alterations in circulating Treg cells, their function and Th17/Treg ratio, other immune cells that affect T cells (e.g., B regulatory cells and natural killer cells), serum and fecal metabolites, microbiota taxa, and serum 25(OH)D, cytokines (e.g., TNF- $\alpha$  & IL-10), and the bone resorption and formation markers (e.g., CTX-1 and P1NP).

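### Protocol Sections 3.0 and 11.0 do not give the same primary outcomes: one list is longer and open-ended, the other names two, and every test is set at 0.05

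*Protocol*

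**What the plan says.** Section 3.0 lists as primary the "change in circulating Th17 cells and their function in" ex vivo work, together with "inflammatory cytokines (e.g., IL-6 & IL-17"). That names four quantities: Th17 abundance, Th17 function, IL-6 and IL-17. The cytokines are given as examples, so the list has no end. The secondary cytokines in the same section (TNF-alpha, IL-10) are also given as examples.

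Section 11.0 opens its primary analysis with linear mixed models, whose stated aim is: "determine if the level of serum IL-6 and T cells (i.e., Th17) at the end of each period is significantly different". The comparison is between the dried plum and control conditions. Its next list is "for secondary outcome measures (i.e., gut microbiota, metabolites, and bone resorption markers"), to be analysed with separate mixed models. The section closes with "For all statistical analyses, alpha will be set at 0.05".

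Other sections treat the unlisted items as live. Under Objective 1 in Section 2.0, "the change in T cell populations and their function as well as inflammatory mediators in response to dried plum will be assessed". The hypothesis in the same section covers Th17 activation as well as abundance. Section 8.0 collects blood "to characterize Th17 and Treg abundance and function". The power statement in Section 11.0 is "80% power to detect an effect size of 0.8 standardized mean difference in the immune response", without naming one outcome.

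**The concern.** A primary set should be readable from the protocol without interpretation, because the SAP and the trial report both take it from there. Here a reader of Section 3.0 finds at least four primaries and a reader of the model sentence in Section 11.0 finds two. IL-17 and Th17 function are primary in the first and unnamed in the second. Because the cytokine list is open, a cytokine named in neither tier has no fixed place and could be called primary once its result is known.

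The 0.05 sentence adds to this. As written, each primary is tested at the full level, however many there turn out to be. The chance of a false primary claim, or the power if several outcomes must succeed, therefore depends on which list is followed.

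**Working it through.** **1. The two lists side by side.**

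| Outcome | Section 3.0 | Section 11.0 |
|---|---|---|
| Th17 abundance | primary | named in primary model |
| IL-6 | primary (example) | named in primary model |
| IL-17 | primary (example) | not named |
| Th17 function | primary | not named |
| Any other cytokine | open in both tiers | not named |

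Four is a minimum, since Section 3.0 does not say how many readouts make up function.

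**2. Is Section 11.0 abbreviating?** Its secondary sentence also leaves out much of Section 3.0's secondary list: Treg cells and their function, the Th17/Treg ratio, B regulatory and natural killer cells, TNF-alpha, IL-10, 25(OH)D and P1NP. So absence from a Section 11.0 sentence does not prove that an outcome was dropped.

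**3. The plan's own power figure.** Inputs from Section 11.0: n = 30, 10% attrition, effect 0.8 SD, 80% power, alpha 0.05. Assumed, because not stated: a two-sided test and the within-person correlation r. Completers: 30 × 0.9 = 27. For an AB/BA crossover, df = 27 − 2 = 25, the effect in SDs of the within-person difference is dz = 0.8/√(2(1 − r)), and the noncentrality is dz × √27. Power from the noncentral t:

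- r = 0: dz = 0.566, power 0.8065
- r = 0.3: dz = 0.676, power 0.922
- r = 0.5: dz = 0.800, power 0.979

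The stated 80% reproduces at r = 0 for one outcome at 0.05.

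**4. If any one p < 0.05 counts as success (illustration).** For k independent outcomes, family-wise error = 1 − 0.95^k.

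- k = 2: 1 − 0.9025 = 0.0975
- k = 4: 1 − 0.8145 = 0.1855

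With equally correlated normal test statistics (correlation assumed, not given):

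| Outcome correlation | Two outcomes | Four outcomes |
|---|---|---|
| 0 | 9.75% | 18.5% |
| 0.5 | 9.1% | 15.6% |
| 0.7 | 8.4% | 13.0% |
| 0.9 | 7.0% | 9.4% |

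**5. If both of two outcomes must succeed (illustration).** Type I error is not inflated, but power falls. With 0.8 SD on each and independent outcomes, joint power is the square of the single-outcome power:

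- r = 0: 0.8065² = 0.650
- r = 0.3: 0.922² = 0.850
- r = 0.5: 0.979² = 0.958

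**The case against.** The strongest reply is that Section 11.0 assigns mixed models to the primary outcomes as a class and then gives examples, with IL-6 standing for the cytokines and Th17 for the T-cell measures. The shortened secondary list supports this reading. It stands to this extent: a reader might infer that the protocol defines two firmly rival primary sets, or that IL-17 and Th17 function have no analysis model, and the text does not bear out either inference. It does not remove the problem. The model sentence speaks of a level, while Sections 3.0 and 8.0 treat function as separate from abundance. Even on the generous reading, the cytokine list stays open.

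A second reply is that multiplicity belongs to the SAP, which is not shown. That is fair. A reader might infer that the protocol lacks a multiplicity procedure and so inflates its type I error. The protocol states no success rule, and an SAP could order the tests with each still run at 0.05. The error rates above are therefore illustrations. But an SAP cannot order a primary family that the protocol leaves unsettled, and the 0.05 sentence as written covers every analysis without distinction.

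A third reply is that the power loss is modest. That depends on r. The 65% joint figure belongs to r = 0 only, and at r = 0.5 little is lost.

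**Conclusion.** The point holds as an inconsistency to reconcile. Section 3.0 names at least four primary outcomes in an open list, Section 11.0 names two of them, and nothing in the protocol says whether the shorter list is shorthand or a decision. Combined with 0.05 for every analysis, this leaves the primary claim open to selection after the results are seen.

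The size depends on rules and correlations that the protocol does not give. If any one success counts, family-wise error runs from 7.0% to 9.75% for two outcomes and from 9.4% to 18.5% for four, over outcome correlations from 0.9 down to 0. If both of two must succeed, power is about 65%, 85% or 96% at within-person correlation 0, 0.3 or 0.5, with 27 completers, independent outcomes and 0.8 SD on each.

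A reader might also infer that the sample size is wrong or that the power statement is in error. Neither follows. The 80% reproduces for a single outcome, and a standardized effect can apply to any continuous immune measure. The textual mismatch is certain; its statistical consequences are conditional. It should be fixed, but it does not invalidate the design.

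**What to change.** 1. In Section 3.0, replace the example cytokines with a closed list in both tiers. Place Th17 function and each cytokine in one tier, and say which readout represents function.
2. Use the identical primary list in the model sentence of Section 11.0.
3. Limit the 0.05 sentence so that the primary family is held at two-sided 0.05. Either name one primary outcome, or test in a fixed sequence whichever outcomes the sponsor keeps as primary. These may be the two already modelled or all of Section 3.0's; the hypothesis in Section 2.0 includes Th17 activation, which bears on whether function stays. Possible wording: *The primary outcomes are [closed list], tested in this order, each at two-sided 0.05; testing stops at the first non-significant result. All other outcomes are secondary or exploratory.*

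Saying which outcome the 0.8 SD power statement refers to would help, but is optional clarification.

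**Cost.** No participants, visits or samples are added. Demoted or later-tested outcomes lose stand-alone primary status. The first outcome in a sequence keeps the full 0.05 and its stated power. With independent outcomes at 0.8 SD each, the chance of confirming the second equals the joint power above (about 65%, 85% or 96%). For the fourth of four it is that figure squared: about 42%, 72% or 92%.
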